## 9.2 Clinical Laboratory Evaluations

The following safety-related laboratory tests will be performed:

- Hematology: Complete blood count (CBC) including white blood cell (WBC) count with differential count, red blood cell (RBC) count, platelet count, hematocrit, hemoglobin, red blood cell indices; neutrophils, lymphocytes, monocytes, eosinophils, and basophils
- Serum Chemistry: Alanine aminotransferase (ALT), alkaline phosphatase, aspartate aminotransferase (AST), bilirubin (total and direct), blood urea nitrogen (BUN)/creatinine, creatinine, lipase, serum creatine kinase, bicarbonate or total carbon dioxide, sodium, potassium, chloride, glucose, total protein, albumin, phosphate, calcium, and amylase
- Urinalysis: WBC, RBC, bacteria, epithelial cells, crystals, and casts.
- Coagulation: Prothrombin time, partial thromboplastin time, and international normalized ratio (INR)
- Other tests for female subjects: HCG; urine and serum

The hematology, serum chemistry, urinalysis, and coagulation tests will be performed at the time points pre-dose and post study-drug. Shift from baseline to worst post-baseline abnormality for these parameters will be presented using the Division of AIDS (DAIDS) standard. For parameters with both low and high ranges, separate summaries to low and high will be assessed.

All clinical laboratory test results will be presented in the data listings. Laboratory values that are outside of the normal reference range will be flagged in the data listings. Abnormal laboratory results will be graded, where applicable, as follows:

PARAMETER	GRADE 1 MILD	GRADE 2 MODERATE	GRADE 3 SEVERE	GRADE 4 POTENTIALLY LIFE-THREATENING
Acidosis	NA	pH $^3$ 7.3 to < LLN	pH < 7.3 without life-threatening consequences	pH < 7.3 with life-threatening consequences
Albumin, Low	3.0 to < LLN	$\geq$ 2.0 to < 3.0	< 2.0	NA

(g/dL; g/L)	30 to < LLN	≥ 20 to < 30	< 20	
Alkaline Phosphatase, High	1.25 to < 2.5 x ULN	2.5 to < 5.0 x ULN	5.0 to < 10.0 x ULN	≥ 10.0 x ULN
Alkalosis	NA	pH > ULN to ≤ 7.5	pH > 7.5 without life-threatening consequences	pH > 7.5 with life-threatening consequences
ALT or SGPT, High	1.25 to < 2.5 x ULN	2.5 to < 5.0 x ULN	5.0 to < 10.0 x ULN	≥ 10.0 x ULN
Report only one				
Amylase (Pancreatic) or Amylase (Total), High	1.1 to < 1.5 x ULN	1.5 to < 3.0 x ULN	3.0 to < 5.0 x ULN	≥ 5.0 x ULN
Report only one				
AST or SGOT, High	1.25 to < 2.5 x ULN	2.5 to < 5.0 x ULN	5.0 to < 10.0 x ULN	≥ 10.0 x ULN
Report only one				
Bicarbonate, Low	16.0 to < LLN	11.0 to < 16.0	8.0 to < 11.0	< 8.0
(mEq/L; mmol/L)	16.0 to < LLN	11.0 to < 16.0	8.0 to < 11.0	< 8.0
Bilirubin				
Direct Bilirubin1, High				
> 28 days of age	NA	NA	> ULN with other signs and symptoms of hepatotoxicity.	> ULN with life-threatening consequences (e.g., signs and symptoms of liver failure)
≤ 28 days of age	ULN to ≤ 1 mg/dL	> 1 to ≤ 1.5 mg/dL	> 1.5 to ≤ 2 mg/dL	> 2 mg/dL
Total Bilirubin, High				
> 28 days of age	1.1 to < 1.6 x ULN	1.6 to < 2.6 x ULN	2.6 to < 5.0 x ULN	≥ 5.0 x ULN

$\leq 28$ days of age	See Appendix A. Total Bilirubin for Term and Preterm Neonates	See Appendix A. Total Bilirubin for Term and Preterm Neonates	See Appendix A. Total Bilirubin for Term and Preterm Neonates	See Appendix A. Total Bilirubin for Term and Preterm Neonates
Calcium, High (mg/dL; mmol/L)				
$\geq 7$ days of age	10.6 to $< 11.5$ 2.65 to $< 2.88$	11.5 to $< 12.5$ 2.88 to $< 3.13$	12.5 to $< 13.5$ 3.13 to $< 3.38$	$\geq 13.5$ $\geq 3.38$
$< 7$ days of age	11.5 to $< 12.4$ 2.88 to $< 3.10$	12.4 to $< 12.9$ 3.10 to $< 3.23$	12.9 to $< 13.5$ 3.23 to $< 3.38$	$\geq 13.5$ $\geq 3.38$
Calcium (Ionized), High (mg/dL; mmol/L)	> ULN to $< 6.0$	6.0 to $< 6.4$	6.4 to $< 7.2$	$\geq 7.2$
Calcium, Low (mg/dL; mmol/L)	> ULN to $< 1.5$	1.5 to $< 1.6$	1.6 to $< 1.8$	$\geq 1.8$
$\geq 7$ days of age	7.8 to $< 8.4$ 1.95 to $< 2.10$	7.0 to $< 7.8$ 1.75 to $< 1.95$	6.1 to $< 7.0$ 1.53 to $< 1.75$	< 6.1 $< 1.53$
$< 7$ days of age	6.5 to $< 7.5$ 1.63 to $< 1.88$	6.0 to $< 6.5$ 1.50 to $< 1.63$	5.50 to $< 6.0$ 1.38 to $< 1.50$	< 5.50 $< 1.38$
Calcium (Ionized), Low (mg/dL; mmol/L)	< LLN to 4.0	3.6 to $< 4.0$	3.2 to $< 3.6$	< 3.2
Cardiac Troponin I, High	NA	NA	NA	Levels consistent with myocardial infarction or unstable angina as defined by the local laboratory
Creatine Kinase, High	3 to $< 6 \times$ ULN	6 to $< 10 \times$ ULN	10 to $< 20 \times$ ULN	$\geq 20 \times$ ULN
Creatinine, High  *Report only one	1.1 to $1.3 \times$ ULN	> 1.3 to $1.8 \times$ ULN OR Increase to 1.3 to	> 1.8 to $< 3.5$ $x$ ULN OR Increase to 1.5 to $< 2.0 \times$ participant's baseline	$\geq 3.5 \times$ ULN OR Increase of $\geq 2.0 \times$ participant's baseline
Creatinine Clearance 2		< 1.5 $\times$ participant's baseline		
	NA	< 90 to 60 ml/min or ml/min/1.73 m 	< 60 to 30 ml/min or ml/min/1.73 m 	< 30 ml/min or ml/min/1.73 m  OR

or eGFR, Low		OR	OR	$\geq 50\%$ decrease from participant's baseline or dialysis needed
*Report only one		10 to $< 30\%$ decrease from participant's baseline	30 to $< 50\%$	
			decrease from participant's baseline	
Glucose				
(mg/dL; mmol/L)				
Fasting, High	110 to 125	> 125 to 250	> 250 to 500	$\geq 500$
	6.11 to $< 6.95$	6.95 to $< 13.89$	13.89 to $< 27.75$	$\geq 27.75$
Nonfasting, High	116 to 160	> 160 to 250	> 250 to 500	$\geq 500$
	6.44 to $< 8.89$	8.89 to $< 13.89$	13.89 to $< 27.75$	$\geq 27.75$
Glucose, Low				
(mg/dL; mmol/L)				
$\geq 1$ month of age	55 to 64	40 to $< 55$	30 to $< 40$	$< 30$
	3.05 to $< 3.55$	2.22 to $< 3.05$	1.67 to $< 2.22$	$< 1.67$
< 1 month of age	50 to 54	40 to $< 50$	30 to $< 40$	$< 30$
	2.78 to $< 3.00$	2.22 to $< 2.78$	1.67 to $< 2.22$	$< 1.67$
Lactate, High	ULN to $< 2.0$	 2.0 x ULN without acidosis	Increased lactate with pH $< 7.3$ without life-threatening consequences	Increased lactate with pH $< 7.3$ with life-threatening consequences
	x ULN without acidosis			
Lipase, High	1.1 to $< 1.5 \times$ ULN	1.5 to $< 3.0 \times$ ULN	3.0 to $< 5.0 \times$ ULN	$\geq 5.0 \times$ ULN
Lipid Disorders				
(mg/dL; mmol/L)				
Cholesterol, Fasting, High				
$\geq 18$ years of age				
	200 to $< 240$	240 to $< 300$	$\geq 300$	NA
	5.18 to $< 6.19$	6.19 to $< 7.77$	$\geq 7.77$	
< 18 years of age	170 to $< 200$	200 to $< 300$	$\geq 300$	NA
	4.40 to $< 5.15$	5.15 to $< 7.77$	$\geq 7.77$	
LDL, Fasting, High				
$\geq 18$ years of age	130 to $< 160$	160 to $< 190$	 190	NA

	3.37 to < 4.12	4.12 to < 4.90	 4.90	
> 2 to < 18 years of age	110 to < 130	130 to < 190	≥ 190	NA
	2.85 to < 3.34	3.34 to < 4.90	≥ 4.90	
Triglycerides, Fasting, High	150 to 300	>300 to 500	>500 to < 1,000	> 1,000
	1.71 to 3.42	>3.42 to 5.7	>5.7 to 11.4	> 11.4
Magnesium  , Low (mEq/L; mmol/L)	1.2 to < 1.4	0.9 to < 1.2	0.6 to < 0.9	< 0.6
	0.60 to < 0.70	0.45 to < 0.60	0.30 to < 0.45	< 0.30
Phosphate, Low (mg/dL; mmol/L)				
> 14 years of age	2.0 to < LLN	1.4 to < 2.0	1.0 to < 1.4	< 1.0
	0.65 to < LLN	0.45 to < 0.65	0.32 to < 0.45	< 0.32
1 to 14 years of age	3.0 to < 3.5	2.5 to < 3.0	1.5 to < 2.5	< 1.5
	0.97 to < 1.13	0.81 to < 0.97	0.48 to < 0.81	< 0.48
< 1 year of age	3.5 to < 4.5	2.5 to < 3.5	1.5 to < 2.5	< 1.5
	1.13 to < 1.45	0.81 to < 1.13	0.48 to < 0.81	< 0.48
Potassium, High (mEq/L; mmol/L)	5.6 to < 6.0	6.0 to < 6.5	6.5 to < 7.0	≥ 7.0
	5.6 to < 6.0	6.0 to < 6.5	6.5 to < 7.0	≥ 7.0
Potassium, Low (mEq/L; mmol/L)	3.0 to < 3.4	2.5 to < 3.0	2.0 to < 2.5	< 2.0
	3.0 to < 3.4	2.5 to < 3.0	2.0 to < 2.5	< 2.0
Sodium, High (mEq/L; mmol/L)	146 to < 150	150 to < 154	154 to < 160	 160
	146 to < 150	150 to < 154	154 to < 160	 160
Sodium, Low (mEq/L; mmol/L)	130 to < 135	125 to < 130	121 to < 125	£ 120
	130 to < 135	125 to < 130	121 to < 125	£ 120
Uric Acid, High (mg/dL; mmol/L)	7.5 to < 10.0	10.0 to < 12.0	12.0 to < 15.0	≥ 15.0
	0.45 to < 0.59	0.59 to < 0.71	0.71 to < 0.89	≥ 0.89
Absolute CD4+ Count, Low (cell/mm  ; cells/L)				
> 5 years of age (not HIV infected)	300 to < 400	200 to < 300	100 to < 200	< 100
	300 to < 400	200 to < 300	100 to < 200	< 100
Absolute Lymphocyte Count, Low (cell/mm  ; cells/L)				

> 5 years of age (not HIV infected)				
	600 to < 650	500 to < 600	350 to < 500	< 350
	0.600 x 10  to	0.500 x 10  to	0.350 x 10  to	< 0.350 x 10 
	< 0.650 x 10 	< 0.600 x 10 	< 0.500 x 10 	
Absolute Neutrophil Count (ANC), Low (cells/mm  ; cells/L)				
> 7 days of age				
	800 to 1,000	600 to 799	400 to 599	< 400
	0.800 x 10  to 1.000	0.600 x 10  to 0.799	0.400 x 10  to 0.599	< 0.400 x 10 
	x 10 	x 10 	x 10 	
2 to 7 days of age	1,250 to 1,500	1,000 to 1,249	750 to 999	< 750
	1.250 x 10  to 1.500	1.000 x 10  to 1.249	0.750 x 10  to 0.999	< 0.750 x 10 
	x 10 	x 10 	x 10 	
≤ 1 day of age	4,000 to 5,000	3,000 to 3,999	1,500 to 2,999	< 1,500
	4.000 x 10  to 5.000	3.000 x 10  to 3.999	1.500 x 10  to 2,999	< 1.500 x 10 
	5.000 x 10 	x 10 	x 10 	
Fibrinogen, Decreased (mg/dL; g/L)	100 to < 200	75 to < 100	50 to < 75	< 50
	1.00 to < 2.00	0.75 to < 1.00	0.50 to < 0.75	< 0.50
	OR	OR	OR	OR
	0.75 to < 1.00 x LLN	≥ 0.50 to < 0.75 x LLN	0.25 to < 0.50 x LLN	< 0.25 x LLN
				OR Associated with gross bleeding
Hemoglobin4, Low (g/dL; mmol/L)				
≥ 13 years of age (male only)	10.0 to 10.9	9.0 to < 10.0	7.0 to < 9.0	< 7.0
	6.19 to 6.76	5.57 to < 6.19	4.34 to < 5.57	< 4.34
≥ 13 years of age (female only)	9.5 to 10.4	8.5 to < 9.5	6.5 to < 8.5	< 6.5
	5.88 to 6.48	5.25 to < 5.88	4.03 to < 5.25	< 4.03

57 days of age to < 13 years of age	9.5 to 10.4	8.5 to < 9.5	6.5 to < 8.5	< 6.5
(male and female)	5.88 to 6.48	5.25 to < 5.88	4.03 to < 5.25	< 4.03
36 to 56 days of age (male and female)	8.5 to 9.6	7.0 to < 8.5	6.0 to < 7.0	< 6.0
	5.26 to 5.99	4.32 to < 5.26	3.72 to < 4.32	< 3.72
22 to 35 days of age (male and female)	9.5 to 11.0	8.0 to < 9.5	6.7 to < 8.0	< 6.7
	5.88 to 6.86	4.94 to < 5.88	4.15 to < 4.94	< 4.15
8 to ≤ 21 days of age (male and female)	11.0 to 13.0	9.0 to < 11.0	8.0 to < 9.0	< 8.0
	6.81 to 8.10	5.57 to < 6.81	4.96 to < 5.57	< 4.96
≤ 7 days of age (male and female)	13.0 to 14.0	10.0 to < 13.0	9.0 to < 10.0	< 9.0
	8.05 to 8.72	6.19 to < 8.05	5.59 to < 6.19	< 5.59
INR, High				
(not on anticoagulation therapy)	1.1 to < 1.5 x ULN	1.5 to < 2.0 x ULN	2.0 to < 3.0 x ULN	≥ 3.0 x ULN
Methemoglobin				
(% hemoglobin)	5.0 to < 10.0%	10.0 to < 15.0%	15.0 to < 20.0%	≥ 20.0%
PTT, High				
(not on anticoagulation therapy)	1.1 to < 1.66 x ULN	1.66 to < 2.33 x ULN	2.33 to < 3.00 x ULN	≥ 3.00 x ULN
Platelets, Decreased	100,000 to	50,000 to	25,000 to	< 25,000
(cells/mm  ; cells/L)	< 125,000	< 100,000	< 50,000	< 25,000 x 10 
	100,000 x 10  to	50,000 x 10  to	25,000 x 10  to	
	< 125,000 x 10 	< 100,000 x 10 	< 50,000 x 10 	
PT, High				
(not on anticoagulation therapy)	1.1 to < 1.25 x ULN	1.25 to < 1.50 x ULN	1.50 to < 3.00 x ULN	≥ 3.00 x ULN
WBC, Decreased				
(cells/mm  ; cells/L)				
> 7 days of age	2,000 to 2,499	1,500 to 1,999	1,000 to 1,499	< 1,000
	2,000 x 10  to 2,499	1,500 x 10  to 1,999	1,000 x 10  to 1,499	< 1,000 x 10 
	x 10 	x 10 	x 10 	

$\leq 7$ days of age	5,500 to 6,999	4,000 to 5,499	2,500 to 3,999	< 2,500
	5.500 x 10  to 6,999	4.000 x 10  to 5,499	2.500 x 10  to 3,999	< 2.500 x 10 
	x 10 	x 10 	x 10 	
Glycosuria (random collection tested by dipstick)	Trace to 1+ or	2+ or > 250 to	> 2+ or > 500 mg	NA
	$\leq 250$ mg	$\leq 500$ mg		
Hematuria (not to be reported based on dipstick findings or on blood believed to be of menstrual origin)	6 to < 10 RBCs per high power field	$\geq 10$ RBCs per high power field	Gross, with or without clots OR With RBC casts OR Intervention indicated	Life-threatening consequences
Proteinuria (random collection tested by dipstick)	1+	2+	3+ or higher	NA

 Direct bilirubin  $> 1.5$  mg/dL in a participant  $< 28$  days of age should be graded as grade 2, if  $< 10\%$  of the total bilirubin.

 Use the applicable formula (i.e., Cockcroft-Gault in mL/min or Schwartz, MDRD, CKD-Epi in mL/min/1.73m^2). Sites should choose the method defined in their study and when not specified, use the method most relevant to the study population.

 To convert a magnesium value from mg/dL to mmol/L, laboratories should multiply by 0.4114.

 Male and female sex are defined as sex at birth. For transgender participants  $\geq 13$  years of age who have been on hormone therapy for more than 6 consecutive months, grade hemoglobin based on the gender with which they identify (i.e., a transgender female should be graded using the female sex at birth hemoglobin laboratory values).

 The most commonly used conversion factor to convert g/dL to mmol/L is 0.6206. For grading hemoglobin results obtained by an analytic method with a conversion factor other than 0.6206, the result must be converted to g/dL using appropriate conversion factor for the particular laboratory.

\*Reminder: Choose the method that selects for the higher grade.

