- Severe organ impairment (e.g., elevated transaminases  $\geq 1,000$  IU/L, impaired consciousness, renal failure [including any subjects with creatinine clearance < 60 mL/min {Cockcroft Gault formula}, or heart impairment] [including any subjects with clinically significant abnormal ECG at Screening])

15. Suspected or confirmed acute illness thought to be caused by a pathogen other than DENV

16. Confirmed or suspected SARS-CoV-2 infection or contact with patients with confirmed SARS-CoV2 infection within 7 days prior to screening

17. ALT or AST > 5x upper limit of normal (ULN) or total bilirubin > 1.5x ULN (Gilbert's syndrome is exempt) or platelet count <80,000/mm^3 at the time of screening

18. Has any other medical disease or condition that in the opinion of the site principal investigator or appropriate sub-investigator, precludes study participation. This includes any acute, subacute, intermittent, or chronic disease or condition that would place the patient at an unacceptable risk of injury, render the patient unable to meet the requirements of the protocol, or interfere with the evaluation of responses or the patient's successful completion of the trial

One-time retests of individual screening laboratory parameters or assessments may be permitted in certain scenarios. Such scenarios may include lab processing error, results inconsistent with subject's historical values/medical history, or other extenuating circumstances such as a recent or intercurrent illness potentially affecting screening laboratory results.

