### 7.3.2 Clinical Laboratory Testing

Clinical laboratory tests will be performed by the study sites' local laboratories. Blood and urine samples will be collected, as per the SOE (Section 3) and will be prepared using standard procedures.

A repeat measurement of clinical laboratory testing is permitted for eligibility determination. Other clinical laboratory retests may be permitted once in certain scenarios with CCI approval. Such scenarios may include laboratory processing error, results inconsistent with subject's historical values/medical history, or other extenuating circumstances such as a recent or intercurrent illness potentially affecting screening laboratory results. The clinical laboratory that will perform the tests will provide the reference ranges for all clinical laboratory parameters. Abnormal clinical laboratory values will be flagged as either high or low (or normal or abnormal) based on the reference ranges for each laboratory parameter.

The following clinical laboratory assessments will be performed at site or laboratory appointed by site:

Hematology	Complete blood count (CBC) including white blood cell (WBC) count with differential count, red blood cell (RBC) count, platelet count, hematocrit, hemoglobin, red blood cell indices
Coagulation	Prothrombin time, partial thromboplastin time, and international normalized ratio (INR)
Serum chemistry	Alanine aminotransferase (ALT), alkaline phosphatase, aspartate aminotransferase (AST), bilirubin (total and direct), blood urea nitrogen (BUN), creatinine, lipase, serum creatine kinase, bicarbonate or total carbon dioxide, sodium, potassium, chloride, glucose, total protein, albumin, phosphate, calcium, and amylase

Urinalysis	Urinalysis will be performed with microscopy at indicated. Additional urinalysis may be performed as clinically indicated. It is not required to have the results from the urinalysis performed at screening before beginning study drug dosing, unless medically necessary to establish eligibility (at investigator's discretion)
Direct viral tests	SARS-CoV-2 rapid test, rapid influenza diagnostic test
Other analyses	Female subjects: Pregnancy test ( $\beta$ -HCG; urine at screening and urine or serum after screening)

Samples for the following laboratory tests will be sent to the sponsor or a designee for analysis:

- Viral Load (as measured by RT-PCR and viral titre)
- Treatment-emergent amino acid substitutions in DENV NS5 polymerase
- DENV Serotype Testing
- NS1 Antigen

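### In the SAP 9.2 grading table, the cells/L limits for low platelets and low white cells are printed 1000 times higher than the cells/mm3 limits beside them, probably through a comma in place of a decimal point.

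*SAP*

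**What the plan says.** SAP 9.2 makes the table the working rule: "Abnormal laboratory results will be graded, where applicable, as follows". The grades feed a planned safety output: "Shift from baseline to worst post-baseline abnormality for these parameters will be presented using the Division of AIDS (DAIDS) standard". Protocol 8.3.3 likewise calls for graded laboratory abnormalities by treatment and for shift tables of severity grade.

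The row "Platelets, Decreased" and the row for decreased WBC both carry the unit label cells/mm3; cells/L. For platelets, the cells/L line of Grade 1 begins "100,000 x 10 9 to", under a cells/mm3 line that starts at 100,000. For WBC over 7 days of age, the Grade 1 cells/L line reads "2,000 x 10 9 to 2,499" (again x 10^9), under 2,000 to 2,499 cells/mm3. In the same table, the neutrophil row over 7 days of age gives "0.800 x 10 9 to 1.000" (x 10^9) under 800 to 1,000 cells/mm3.

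On the source of the results, Protocol 7.3.2 says: "Clinical laboratory tests will be performed by the study sites' local laboratories". Neither document fixes a reporting unit for platelets or white cells, says which of the two lines governs, or requires conversion before grading.

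**The concern.** The two lines in a cell should express one limit in two units. In these two rows they do not, so the same blood count gets different grades depending on which line is programmed. Platelets and white cells are safety measures of obvious interest in dengue, and the protocol uses the platelet count as an entry limit. If a laboratory reports in 10^9/L and the programmer takes the SI line as printed, mild and severe falls become indistinguishable. The grade summaries and shift tables for those subjects then no longer describe what happened to them.

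**Working it through.** **Conversion.** 1 L = 10^6 mm3, so cells/L = cells/mm3 x 10^6. The value in units of 10^9/L is therefore the cells/mm3 value divided by 1000.

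**Test on rows that should agree.** For neutrophils over 7 days of age, 800/1000 = 0.800 and 1,000/1000 = 1.000, as printed. For lymphocytes, 600/1000 = 0.600 and 350/1000 = 0.350, as printed. The ratio of printed to converted value is 1.0 for every limit in these two rows.

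**The two rows in question** (SI values in 10^9/L; all inputs from the SAP 9.2 table):

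| Row and grade | cells/mm3 line | SI line as printed | SI line converted | Ratio |
|---|---|---|---|---|
| Platelets, Grade 1 | 100,000 to <125,000 | 100,000 to <125,000 | 100 to <125 | 1000 |
| Platelets, Grade 2 | 50,000 to <100,000 | 50,000 to <100,000 | 50 to <100 | 1000 |
| Platelets, Grade 3 | 25,000 to <50,000 | 25,000 to <50,000 | 25 to <50 | 1000 |
| Platelets, Grade 4 | <25,000 | <25,000 | <25 | 1000 |
| WBC, Grade 1 | 2,000 to 2,499 | 2,000 to 2,499 | 2.000 to 2.499 | 1000 |
| WBC, Grade 2 | 1,500 to 1,999 | 1,500 to 1,999 | 1.500 to 1.999 | 1000 |
| WBC, Grade 3 | 1,000 to 1,499 | 1,000 to 1,499 | 1.000 to 1.499 | 1000 |
| WBC, Grade 4 | <1,000 | <1,000 | <1.000 | 1000 |

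**Which line has the right scale.** The protocol excludes patients with "platelet count <80,000/mm 3 at the time of screening" (3 is an exponent). That is 80 x 10^9/L, which lies within Grade 2 on the cells/mm3 line. The SI line as printed would put it in Grade 4. The cells/mm3 line is the sound one.

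**Grades under each line** (counts in 10^9/L):

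| Count | cells/mm3 line | SI line as printed | SI line converted |
|---|---|---|---|
| Platelets 20 | 4 | 4 | 4 |
| Platelets 40 | 3 | 4 | 3 |
| Platelets 80 | 2 | 4 | 2 |
| Platelets 110 | 1 | 4 | 1 |
| WBC 0.8 | 4 | 4 | 4 |
| WBC 1.2 | 3 | 4 | 3 |
| WBC 1.7 | 2 | 4 | 2 |
| WBC 2.2 | 1 | 4 | 1 |

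To escape Grade 4 on the printed SI line, platelets would have to reach 25,000 x 10^9/L and WBC 1,000 x 10^9/L.

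**Effect on a shift table**, if only abnormal results are graded:

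- A subject who enters at 80 and falls to 40 moves from Grade 2 to Grade 3. The printed SI line shows Grade 4 to Grade 4, so a real worsening disappears.
- A subject who starts within the reference range and falls to 110 (taken here as below the local range) moves from no grade to Grade 1. The printed SI line shows a new Grade 4, so a mild fall looks life-threatening.

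**Likely cause.** Two infant rows mix comma and point within one SI range: WBC up to 7 days of age runs from 5.500 to 6,999, and neutrophils up to 1 day of age from 1.500 to 2,999 (both x 10^9). Reading the comma as a decimal point gives 100.000 and 2.000, and all the platelet and WBC limits above then come out right.

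**The case against.** The strongest reply is that this is punctuation, not a wrong threshold. The infant rows show commas standing where points are meant. The text available here was read from PDF by a program, and other symbols in the table are visibly corrupted. The intended limits are recoverable, because the correct cells/mm3 value stands in the same cell and the SAP and protocol both name the DAIDS scale. A run that put every abnormal SI result in Grade 4 would be conspicuous.

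Most of this stands. It explains the cause and lowers the risk, but it does not make the printed limits usable. On the line directly above, the same comma is a thousands separator, and it appears in every adult platelet and WBC SI limit of 1,000 or more.

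Three stronger readings are tempting, and the documents do not support them:

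- A reader might infer that all SI results, including normal ones, become Grade 4 and that no subject shows any shift. SAP 9.2 provides for grading abnormal results, where applicable, so a normal baseline need not be graded. Results in cells/mm3 are not affected at all.
- A reader might infer from the correct neutrophil and lymphocyte rows that the comma cannot be a decimal mark. The infant rows contradict that.
- A reader might infer that units will be mixed across the approximately 40 sites. The protocol says only that laboratories are local; mixed reporting is possible but not stated.

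The table's closing reminder to choose the method giving the higher grade does not settle which unit line governs. Its asterisk belongs to the creatinine and creatinine-clearance entries.

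**Conclusion.** The discrepancy holds as a factor of exactly 1000 in every cells/L limit of the platelet row and of the WBC row for ages over 7 days, which are the rows that apply to adults aged 18 to 55. Its effect depends on two conditions: some results are graded in 10^9/L, and the SI line is programmed as printed. If both hold, every abnormal platelet or WBC result so graded is Grade 4, and the shift tables are distorted for those results. The number of subjects affected cannot be estimated, because the reporting unit is not given. The conclusion also assumes that the commas are in the source page and are not a reading artefact.

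Severity is minor to moderate. The primary endpoint, sample size, analysis populations and cells/mm3 grades are untouched, and routine checking would probably expose the error. It is still worth correcting, because the table is the stated grading rule for a planned safety analysis.

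**What to change.** First confirm the commas on the original SAP page. If they are there, make the SI lines agree with the SAP's own cells/mm3 limits:

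- Platelets (x 10^9/L): Grade 1, 100 to <125; Grade 2, 50 to <100; Grade 3, 25 to <50; Grade 4, <25.
- WBC over 7 days of age (x 10^9/L): Grade 1, 2.000 to 2.499; Grade 2, 1.500 to 1.999; Grade 3, 1.000 to 1.499; Grade 4, <1.000.

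Add one sentence stating that local laboratory results are converted to a single unit before grading. The infant rows can be corrected or deleted, since they do not apply to this trial.

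The cost is two table rows and one sentence. No grading limit changes in substance, and no data collection or other analysis is affected.
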